11.1. Co-primary Endpoints and Analysis

11.1.1. Progression Free Survival

Progression-free survival will be calculated as the time from randomization to the first documented progression confirmed by a blinded, independent Response Adjudication Committee or death due to any cause during or after the treatment period, whichever occurs first. The progression date will be assigned to the earliest time when any progression is observed without prior missing assessments. If withdrawal of consent or lost to follow-up occurs before documented progression or death, then these observations will be censored at the date when the last complete tumor assessments determined a lack of progression.

For subjects who do not develop progressive disease at the time of analysis, if the response from the last visit was ‘not evaluable’, the most prior visit date with complete evaluation indicating no progressive disease will be used as the censor date. These rules are based on FDA guidance for cancer trial endpoints [REDACTED] and the following table specifies the application of the guidance for various common situations for the calculation of PFS.

Detailed decision rules for the primary and a sensitivity analysis of PFS are summarized in the following tables:

Table 2: Primary Analysis of PFS

Situation	Date of Progression or Censoring	Situation Outcome
No baseline tumor assessments	Randomization	Censored
Progression documented between scheduled visits	Earliest of: 
 • Date of physical examination for lymphadenopathies, spleen and liver showing: 
 ○ appearance of new lymphadenopathies or new organ infiltration or ○ increase by 50% or more in the greatest determined diameters of previously existing lymphadenopathies ○ increase by 50% or more in liver or spleen size • Date of lab test showing 50% or more increase in lymphocytes • Date of post-treatment lab test showing occurrence progression of cytopenia attributable to CLL • Date of test confirming transformation to a more aggressive histology 	Progressed
No progression	Date of last adequate assessment with evidence of no progression	Censored
Study discontinuation for reasons other than disease progression	Date of last adequate assessment with evidence of no progression	Censored
New anticancer treatment started with no claim of progression	Date of last adequate assessment with evidence of no progression prior to the start of new anticancer treatment	Censored
Death before first PD assessment while on	Date of death	Progressed

study		
-------	--	--

Table 2: Primary Analysis of PFS (Continued)

Situation	Date of Progression or Censoring	Situation Outcome
Death or progression after an extended lost-to-follow-up time (two or more missed assessments) while on study	Date of last adequate assessment with evidence of no progression	Censored
Death between adequate assessment visits while on study	Date of death	Progressed
Death within two months after study discontinuation	Date of death	Progressed
Death beyond two months after study discontinuation	Date of last adequate assessment with evidence of no progression	Censored

Table 3: Sensitivity Analysis for PFS

Situation	Date of Progression or Censoring	Situation Outcome
No baseline tumor assessments	Randomization	Censored
Progression documented between scheduled visits	Date of next scheduled visit	Progressed
No progression	Date of last adequate assessment with no evidence of progression	Censored
Study discontinuation for reasons other than disease progression	Date of last adequate assessment with no evidence of progression during follow-up	Censored
New anticancer treatment started with no claim of progression	Date of last adequate assessment with no evidence of progression during follow-up regardless of new anticancer treatment	Censored
Death before first PD assessment while on study	Date of death	Progressed
Death between adequate assessment visits while on study	Date of death	Progressed

Table 3: Sensitivity Analysis for PFS (Continued)

Situation	Date of Progression or Censoring	Situation Outcome
Death or progression after an extended lost-to-follow-up time (two or more missed assessments) while on study	Date of last adequate assessment with no evidence of progression	Censored
Death within two months after study discontinuation	Date of death	Progressed
Death beyond two months after study discontinuation	Date of study discontinuation visit	Censored

Kaplan-Meier product limit methods will be used to estimate the survivorship functions for the time-to-event endpoints (e.g., PFS, time to response, and OS). A two-sided log-rank test stratified by the 3 strata used in the randomization will be used as the primary analytic method to compare survivorship functions for time-to-event variables in the 2 treatment groups. In terms of the survivorship functions for each treatment group, the hypotheses of interest were:

$$H_0: F_A(t) = F_P(t) \text{ for all } t$$

Versus

$$H_1: F_P(t) \neq F_A(t) \text{ for all } t$$

where F_P is the survivorship function for placebo and F_A is the survivorship function for lenalidomide.

Median PFS will be estimated using Kaplan-Meier estimates, and the 95% confidence intervals (CI) will be computed using the method of Brookmeyer and Crowley. Hazard ratio will be calculated using Cox model stratified for the 3 strata (i.e., response to second-line induction chemotherapy, age, and presence of at least one prognostic factor) to account for the stratified randomization. The Cox model will also be used to identify prognostic factors.

Cross-tabulations will be provided by treatment group to summarize improvements from the best response during induction therapy.

For the primary analysis, the comparison of PFS between the treatment arms using the stratified log rank test, the overall two-sided significance level is 2.5%.

An unstratified log-rank test will also be performed as a secondary analysis for PFS, in addition to the stratified analysis described above.

11.1.2. Overall Survival (OS)

Overall survival is calculated as the time from randomization to death from any cause. OS will be censored at the last date that the subject was known to be alive for subjects who were alive at the time of analysis and for subjects who were lost to follow-up before death was documented.

The analysis of OS will include survival information for all randomized subjects. Subjects who discontinued from the treatment phase of the study and who had possibly received other anti-cancer therapies and then subsequently died will be included in the analysis as death. However, sensitivity analyses will be performed in which these subjects will be censored at the date of the first dose date of the anti-cancer therapy.

OS will be compared between treatment arms using the stratified log-rank test at 2-sided 0.025 alpha level. The same methods used for the PFS analysis will be used for the OS analysis.

11.2. Secondary Endpoints and Analysis

11.2.1. Change in Tumor Response

Tumor response, including PD, will be assessed according to the IWCLL guidelines for the diagnosis and treatment of chronic lymphocytic leukemia (Hallek, 2008). Subjects' tumor response status change based on the best response during the treatment period relative to the response at baseline (i.e., from PR, nPR, CRi, CR, MRD-negative CR to PD, nPR, CRi, CR, MRD-negative CR) will be compared in the two arms using Van Elteren's test at a two-sided 0.05 significance level stratified for the 3 strata used at randomization. Responses from subjects after they received other anti-cancer treatments will not be counted; however, these subjects will be included in the denominator. Cross tabulations will be provided to summarize response frequency change comparing to baseline.

11.2.2. Duration of Improved Response

For those subjects who show improvement from their best response achieved during induction therapy while on study treatment (e.g. PR to CR or CR to MRD-CR), the duration of the improved response will be summarized. The duration of improved response will be calculated at the time from first improvement to the time of disease progression. Duration of improved response will be censored at the date of last assessment showing no worsening from the improved response. A two-sided unstratified log rank test at 0.05 significance level will be used to test the duration of improved response between the two treatment arms.

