Secondary analyses will be performed to characterize change in tumor response, duration of improved response, HRQL, and PFS2. If either of the co-primary endpoints is significant, a fixed sequence testing procedure will be used for the secondary endpoints with the following order: tumor response, duration of response. The Kaplan-Meier procedure will be used to characterize the time-to-event curves in these analyses when there is censoring. Stratified log ranks tests will be used to compare the time-to-event curves. Analysis of variance/covariance (ANOVA/ANCOVA) will be used to compare HRQL and EQ-5D total scores and subscores across the two treatment arms. Otherwise, summary statistics (mean, standard deviation, median, minimum and maximum) and relevant confidence intervals will be provided.

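### Duration of improved response ends at progression but is censored on loss of the improvement, so event and censoring refer to different states

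*SAP*

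**What the plan says.** SAP section 11.2.2 sets up the endpoint in four steps.

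- **Who:** "For those subjects who show improvement from their best response achieved during induction therapy while on study treatment".
- **Event:** "The duration of improved response will be calculated at the time from first improvement to the time of disease progression".
- **Censoring:** "Duration of improved response will be censored at the date of last assessment showing no worsening from the improved response".
- **Test:** "A two-sided unstratified log rank test at 0.05 significance level will be used to test the duration of improved response".

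SAP section 11 makes this more than a description. If either co-primary endpoint is significant, "a fixed sequence testing procedure will be used for the secondary endpoints with the following order: tumor response, duration of response". On estimation it adds: "The Kaplan-Meier procedure will be used to characterize the time-to-event curves in these analyses when there is censoring".

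Neither section makes loss of the improved response an event, mentions death for this endpoint, or gives a sensitivity analysis for it. The current protocol, section 7.2, lists only safety and PFS2 as secondary endpoints.

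**The concern.** A time-to-event endpoint is coherent when subjects without the event are censored at the last time they were known to be free of that same event. Here the event is progression, but a subject leaves the risk set on losing the improvement. Two things follow.

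First, loss of the improvement without progression never counts as a failure. It only ends follow-up. Loss is likely to precede progression, so Kaplan-Meier's assumption that censored subjects face the same future risk as those still followed is doubtful.

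Second, the rule is incomplete. For a subject who loses CR and progresses later, one programmer could count the progression at its date and another could stop the subject at the last CR assessment. SAP section 5.3 calls for independent programming of key efficacy tables, and both codings would be defensible. At stake is what the reported median and the 0.05 test refer to.

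**Working it through.** The plan gives no figure to reproduce. SAP section 6.1 sizes only OS and PFS, and nothing is stated for this endpoint. The check is therefore textual, followed by an illustration.

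**1. Event and censoring state, by endpoint**

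| SAP endpoint | Event | Censored when last known to be |
|---|---|---|
| PFS (11.1.1) | Progression or death | Without progression |
| OS (11.1.2) | Death | Alive |
| PFS2 (11.2.4) | Second progression or death | Alive without second progression |
| Duration of improved response (11.2.2) | Progression | Not worse than the improved response |

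Only the last row mixes two states.

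**2. Subject courses under 11.2.2**

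- Still improved at cutoff: censored at the last assessment. No problem.
- Improved, then progresses directly: event. No problem.
- PR to CR to PR, never progresses: censored at the last CR assessment, although later visits show no progression.
- PR to CR to PR, then progresses: not addressed. *Count* reading: event at progression. *Drop* reading: censored at the last CR assessment.

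**3. Closed form, drop reading**

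Let λ be the progression hazard and kλ the hazard of losing the improvement without progressing, both constant and independent, with M = ln 2/λ.

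- Median time in improved response = ln 2/(λ + kλ) = M/(1 + k).
- Kaplan-Meier median with losses censored = ln 2/λ = M.
- Overstatement factor = 1 + k.

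Inputs: M = 20 and 32.3 months, the PFS medians in SAP 6.1. Applying them to improved responders is an assumption. The values k = 0.25, 0.5 and 1.0 are also assumed.

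- M = 20: 20/1.25 = 16.0, 20/1.5 = 13.3, 20/2 = 10.0, against 20 from the rule.
- M = 32.3: 25.84, 21.53 and 16.15, against 32.3 from the rule.
- Factors: 1.25, 1.5 and 2.0.

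**4. Simulation, both readings**

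Each setting has 200,000 subjects, with administrative cutoff uniform over 24 to 60 months (assumed). Kaplan-Meier medians in months, M = 20:

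| k | Progression hazard after loss | Time in improved response | Drop | Count | Time to progression |
|---|---|---|---|---|---|
| 0.25 | same | 16.0 | 20.0 | 19.4 | 20.0 |
| 0.25 | doubled | 16.1 | 20.1 | 18.7 | 18.9 |
| 0.5 | same | 13.4 | 20.0 | 18.8 | 20.0 |
| 0.5 | doubled | 13.4 | 20.1 | 17.6 | 17.9 |
| 1.0 | same | 10.0 | 20.0 | 18.0 | 20.0 |
| 1.0 | doubled | 10.0 | 19.9 | 16.1 | 16.6 |

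With M = 32.3 the pattern is the same: time in improved response 16.0 to 25.9, drop 32.0 to 32.5, count 24.8 to 30.7, time to progression 26.8 to 32.4.

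- Both readings exceed time in improved response in every row.
- The count reading falls below time to progression in every row. Between loss and cutoff, only those who will progress stay at risk; the others are moved back to the date of loss.
- The drop reading matches time to progression only when loss says nothing about later progression. When the hazard doubles after loss, it runs long (for example 20.1 against 17.9).

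**5. Effect between arms**

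- Hold direct progression at M = 20 and let k be 0, 0.5, 1 and 2, with the same hazard after loss. Count gives 20.0, 18.8, 18.0 and 16.8. Drop gives 20.0 throughout.
- Instead fix the median improved response at 12 months, let 30% or 50% of losses be regressions with progression a median of 12 months later, and take the cutoff as uniform over 12 to 48 months. Count gives 15.6 and 18.4, against true times to progression of 16.3 and 19.9.

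More regression lowers the median in the first set-up, leaves it unchanged under drop, and raises it in the second.

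**The case against.** The strongest reply is that the SAP does name its quantity, time from first improvement to progression, and that the censoring sentence is loose wording for no progression. Read that way, nobody is censored at loss and the repair is a word or two. That reading is plausible and is one of the two repairs below. It is not what the sentence says, though, and a program would follow the sentence.

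A second reply also stands in part. The progression criteria in protocol section 8.1 are broad. For a subject in CR, a new node above 1.5 cm, new hepatomegaly or splenomegaly, or a lymphocyte rise of at least 50% with at least 5,000 B cells per µL already counts as progression. Loss without progression is then mostly marrow findings, smaller blood changes or return of MRD. It may be uncommon, and the documents do not say.

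Three stronger conclusions are tempting and are not supported.

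- A reader might infer that the duration is simply overstated. That is true of time in the improved response. Against time to progression, the count reading runs short.
- A reader might infer that the arm with more regression looks better. Step 5 shows it can look better, worse or the same. Where it looks better, that arm really does progress later.
- A reader might infer that a subject who loses CR and progresses much later is credited up to progression. The SAP is silent on that course.

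**Conclusion.** The definition is wrong as written, in a limited way. Its event and censoring rule refer to different states, one common course is left uncoded, and censoring is triggered by something probably related to prognosis. The result is too long for time in the improved response under either reading. It is too short for time to progression if later progressions are counted. If they are not counted, it is unbiased for time to progression only in the special case where loss carries no information.

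The size is unknown. The factors of 1.25 to 2.0 and the medians above rest on assumed loss rates, constant hazards and an assumed cutoff, and should be read only as showing direction. The direction of any effect on the log-rank comparison cannot be determined.

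The reach is small. The endpoint comes second in the fixed sequence, after tumor response, and OS and PFS do not depend on it. The protocol following Amendment #10 no longer lists it, so it may already be obsolete. While SAP 11.2.2 stands, its rule needs correcting.

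**What to change.** Choose one quantity and make both sentences of SAP 11.2.2 refer to it.

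- **(a) Time from first improvement to progression.** Keep progression as the event. Censor subjects without progression at their last adequate assessment showing none, as in the PFS rules, and rename the endpoint accordingly.
- **(b) Time in the improved response.** The event is the first documented worsening from the improved response category, or progression, whichever comes first. Censor only subjects still in the improved response, at their last adequate assessment.

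Under either option, state how death without progression is coded, and use one name for the endpoint in SAP sections 5.2, 11 and 11.2.2. If Amendment #10 removed the endpoint, say so in the SAP instead.

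The cost is a few sentences and no change to the primary analysis. Option (a) needs nothing beyond the progression data. Option (b) uses the response categories that protocol section 8.1 has investigators record every 28 days on treatment. Dating loss of CR or of MRD negativity, however, depends on marrow, CT or flow results, and the current protocol uses these during treatment only where appropriate, as local assessments. The SAP should say what counts as an adequate assessment for that purpose.

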11.2.3. Health-Related Quality of Life (HRQL)

For Health-Related Quality of Life (HRQL) by Functional Assessment of Cancer Therapy-Leukemia (FACT-Leu) and EQ-5D, changes from baseline in overall score and sub-scores will be analyzed using repeated measures of ANOVA/ANCOVA using the baseline scores as covariates where appropriate.

Various schemes will be assessed for missing data imputation if needed.

11.2.4. Progression Free Survival 2 (PFS2)

PFS2 is defined as the time from randomization to second objective disease progression, or death from any cause, whichever occurred first. Patients alive and for whom a second objective disease

progression has not been observed should be censored at the last time known to be alive and without second objective disease progression. In situations where OS and PFS2 cannot reliably be determined, it may be possible to rule out significant lack of efficacy of further treatments by looking at the outcome of the next line therapy. For this analysis, an event is defined as second objective disease progression, or death from any cause, or the start of the CLL therapy after next line treatment, whichever occurred first [REDACTED]

11.3. Subgroup Analysis

The effect of treatment on the efficacy endpoints of PFS and OS will be compared between treatment arms within subgroups defined by the following variables:

- Age group (≤ 70 , > 70 years)
- Response to 2nd line therapy: (PR, nPR, CRi or CR *versus* MRD-negative CR)
- Presence of at least one of the following poor prognostic factors: 11q deletion, 17p deletion, unmutated IgV_H or $\beta 2M > 4.0$ mg/L (Yes versus No versus Unknown)

The methods described in Sections 11.1.1 and 11.2.1 for the endpoints of PFS and OS respectively, will be used for each subgroup.

[REDACTED]

12. SAFETY ANALYSIS

All safety analyses will be based on all treated subjects and will be presented by treatment group. Safety measurements will include adverse events, clinical laboratory information, vital signs, and deaths. All analyses of safety data will be conducted using the safety population unless specified otherwise.

12.1. Adverse Events

Adverse events (AE) will be classified using the Medical Dictionary for Regulatory Activities (MedDRA) classification system. The severity of the toxicities will be graded according to the NCI CTCAE version 3.0 whenever possible.

The adverse event of infection will also be analyzed according to the grading system as recommended by the IWCLL guidelines for the diagnosis and treatment of CLL [REDACTED] (Appendix 22.4).

Treatment emergent adverse events (AEs) will be summarized by treatment group and overall. A treatment emergent adverse event is defined as any AE occurring or worsening on or after the first treatment of any study drug, and within 30 days after the last dose of the last study drug received. Adverse events will be summarized by treatment arm and overall. Adverse events are documented on the CRF together with their severity, according to the NCI CTCAE version 3.0 or higher, also referred to as NCI toxicity grading. For the categorization of the adverse events, the Medical Dictionary for Regulatory Activities (MedDRA[®]) dictionary (version 16.0) will be used.

AE frequency will be tabulated by body system, MedDRA preferred term for each treatment regimen during the Treatment Phase as well as for the Follow-up Phase when appropriate. In the by-subject analysis, a subject having the same event more than once will be counted only once. AEs will be summarized by worst NCI CTCAE version 3.0 grade. In the case that the AEs or event frequencies are judged to be clinically important, an exact test may be used to analyze the difference between the treatment groups. In addition, AEs of special interest (Event of Interest),

including second primary malignancies (SPM), will be defined and summarized by treatment arm.

AEs leading to death or to discontinuation from treatment, events classified as NCI CTCAE version 3.0 Grade 3 or higher, study-drug-related events, serious adverse events (SAEs) and events of interest (including second primary malignancies) will be summarized separately.

Individual AE listings by subject will be provided.

[REDACTED]

Adverse events (AE) will be classified using the Medical Dictionary for Regulatory Activities (MedDRA) classification system. The severity of the toxicities will be graded according to the NCI CTCAE version 3.0 whenever possible.

The adverse event of infection will also be analyzed according to the grading system as recommended by the IWCLL guidelines for the diagnosis and treatment of CLL [REDACTED] (Appendix 22.4).

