**After Study Discontinuation:**

Upon discontinuation of study drug, subjects will be followed every 24 weeks for survival, information on other CLL treatments, response to next therapy and progression following next therapy, and second primary malignancies (reported as SAEs). Subjects will be followed until all subjects in the study have been followed for at least 5 years from the last randomization, October 2020 (or have died/become lost to follow-up before 5 years).

FCBP with regular menstrual cycles discontinued from treatment must have a pregnancy test on day 28 after the treatment discontinuation visit. FCBP with irregular cycles discontinued from treatment must have a pregnancy test on days 14 and 28 after the treatment discontinuation visit.

SAEs will continue to be collected for the first 30 days after the treatment discontinuation visit. Following 30 days post the treatment discontinuation visit, only SAEs related to maintenance therapy will be collected for the study duration. Second primary malignancies must be reported as SAEs. This includes any second primary malignancy, regardless of causal relationship to study medication, occurring at any time for the duration of the study, from the time of signing the informed consent up to and including progression free follow-up and survival follow-up.

[REDACTED]

[REDACTED]

[REDACTED]

[REDACTED]

[REDACTED]

[REDACTED]

[REDACTED]

[REDACTED]

[REDACTED]

[REDACTED]

[REDACTED]

[REDACTED]

[REDACTED]

[REDACTED]

[REDACTED]

[REDACTED]

[REDACTED]

[REDACTED]

[REDACTED]

[REDACTED]

[REDACTED]

[REDACTED]

[REDACTED]

[REDACTED]

[REDACTED]

[REDACTED]

[REDACTED]

[REDACTED]

[REDACTED]

[REDACTED]

[REDACTED]

[REDACTED]

[REDACTED]

[REDACTED]

[REDACTED]

[REDACTED]

[REDACTED]

[REDACTED]

[REDACTED]

[REDACTED]

[REDACTED]

[REDACTED]

[REDACTED]

[REDACTED]

[REDACTED]

[REDACTED]

[REDACTED]

[REDACTED]

[REDACTED]

[REDACTED]

[REDACTED]

[REDACTED]

[REDACTED]

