### 16.7. Safety Evaluation

All subjects who receive at least one dose of study medication will be included in the safety analyses.

Adverse events (AE) will be classified using the Medical Dictionary for Regulatory Activities (MedDRA) classification system. The severity of the toxicities will be graded according to the NCI CTCAE version 3.0 whenever possible.

The adverse event of infection will also be analyzed according to the grading system as recommended by the IWCLL guidelines for the diagnosis and treatment of CLL [REDACTED] ([Appendix 22.4](#)).

AE frequency will be tabulated by body system, MedDRA preferred term for each treatment regimen during the Treatment Phase. In the by-subject analysis, a subject having the same event more than once will be counted only once. AEs will be summarized by worst NCI CTCAE version 3.0 grade. AEs leading to death or to discontinuation from treatment, events classified as NCI CTCAE version 3.0 Grade 3 or higher, study-drug-related events, serious adverse events (SAEs), and events of interest (including second primary malignancies) will be summarized separately.

Laboratory data will be graded according to NCI CTCAE version 3.0 severity grade. Cross tabulations will be provided to summarize frequencies of abnormalities.

For vital sign and body weight data, means, medians, standard deviations, minimum, and maximum values will be provided.

Graphical displays will be provided where useful to assist in the interpretation of results.

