### **Immediate reporting of serious adverse events**

Any AE that meets the criterion for a SAE requires the completion of a SAE Report Form in addition to being recorded on the AE pages of the CRF. The Investigator(s) is required to ensure that the data on these forms is accurate and consistent. This applies to all SAEs, regardless of relationship to study drug, that occur during the study, those made known to the Investigator(s) within 30 days after a subject's treatment discontinuation visit, and those made known to the investigator(s) at anytime that are suspected of being related to study drug.

Second primary malignancies will be monitored as events of interest and must be reported as serious adverse events. This includes any second primary malignancy, regardless of causal relationship to study medication, occurring at any time for the duration of the study, from the time of signing the ICF up to and including any follow-up, observation and/or survival follow-up period. In this study, subjects will be followed until all subjects in the study have been followed for at least 5 years from the last randomization, October 2020 (or have died/become lost to follow-up before 5 years). Events of second primary malignancy are to be reported using the SAE report form and must be considered an "Important Medical Event" even if no other serious criteria apply; these events must also be documented in the appropriate page(s) of the CRF and subject's source documents. Documentation of the diagnosis of the second primary malignancy must be provided at the time of reporting as a serious adverse event (eg, any confirmatory histology or cytology results).

Grade 4 hematologic abnormalities are expected in patients with CLL, and are also observed in patients receiving lenalidomide. The investigator will use their judgement to classify the seriousness of laboratory abnormality events. Laboratory values will be captured within the study database and will be reviewed on an ongoing basis by the sponsor and (provided that it is determined that any observed individual abnormalities or patterns of abnormalities do not warrant prompt communication to Health Authorities) will be reported to Health Authorities in periodic safety reports.

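### SAP 12.1 gives the second primary malignancy summary no time window and no time-at-risk denominator, although the protocol collects these events to the end of survival follow-up

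*SAP*

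**What the plan says.** **Collection.** Protocol 8.1 (After Study Discontinuation) requires reporting, as a serious adverse event, of "any second primary malignancy, regardless of causal relationship to study medication, occurring at any time for the duration of the study". Appendix 22.1 (immediate reporting of serious adverse events) gives the same span: "occurring at any time for the duration of the study, from the time of signing the ICF up to and including any follow-up". Protocol Table 2 schedules SPM assessment at the 24-weekly survival visits, where the general adverse event row is blank.

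**Analysis.** SAP 12.1 defines a treatment-emergent adverse event as "any AE occurring or worsening on or after the first treatment of any study drug, and within 30 days after the last dose". It then tabulates adverse event frequency by regimen "during the Treatment Phase as well as for the Follow-up Phase when appropriate", counting each subject once per event. For SPMs it says that adverse events of special interest, "including second primary malignancies (SPM), will be defined and summarized by treatment arm", and later that "events of interest (including second primary malignancies) will be summarized separately". Protocol 16.7 states: "AE frequency will be tabulated by body system, MedDRA preferred term for each treatment regimen during the Treatment Phase". The same section also summarizes SPMs separately, with no phase named.

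For deaths, by contrast, SAP 12.5 commits to a second set of tables covering the follow-up phase. SAP 6.4.1 takes percentages over numbers of subjects or of non-missing observations. No visible sentence gives the SPM summary a start, an end, or person-time.

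**The concern.** SPM is the safety event for which the protocol keeps collecting data long after dosing ends, regardless of causality. How it is counted therefore matters more than for ordinary adverse events.

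Two things are left open. First, a programmer could build the SPM table on the 30-day window, the only one the section defines in numbers, and still comply with the SAP. An SPM on day 31 after last dose would be reportable under the protocol and absent from that table. Second, a frequency by arm takes no account of time at risk. The design expects the arms to differ in both time to progression and survival, so equal SPM hazards would produce unequal counts. A reader could take that inequality for a drug effect, or miss a real effect behind it.

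**Working it through.** **The plan's own figures.** The documents give no figure for SPMs inside or outside any window. The design inputs agree with one another: 20/32.3 = 0.619 and 3/4.84 = 0.620, against the stated hazard ratio of 0.62. Power at 160 events, two-sided alpha 0.025, by Schoenfeld's formula is Φ(√160/2 × |ln 0.62| − 2.241) = Φ(0.782) = 78.3%, close to the stated 80% (interim look not modelled).

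**Inputs.**
- Median PFS 20 and 32.3 months, median OS 36 and 58.08 months (4.84 × 12), placebo and lenalidomide, exponential: SAP 6.1.
- Dosing up to progression: SAP 5.1. Last dose is taken as the PFS event.
- At least 5 years of follow-up: SAP 5.1, so T = 60 months. T = 84 is an assumption to show the range.
- Window extension w = 30/30.4 = 0.987 months, using the SAP 6.4.3 month length.
- Assumed: a constant SPM hazard, equal in the two arms, in all living subjects.

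**Time alive per subject.** A = (1 − exp(−λ_OS·T))/λ_OS, with λ_OS = ln 2/median. At T = 60:
- Placebo: λ = 0.019254, A = (1 − 0.3150)/0.019254 = 35.6 months.
- Lenalidomide: λ = 0.011934, A = (1 − 0.4887)/0.011934 = 42.8 months.

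**Time inside the 30-day window.** W is the integral from 0 to T of the smaller of S_PFS(t − w) and S_OS(t). The smaller of the two is an upper limit on the proportion both alive and in the window, so the loss is, if anything, slightly understated. The OS curve is the smaller until t* = λ_PFS·w/(λ_PFS − λ_OS), about 2.22 months in both arms. At T = 60:
- Placebo: λ_PFS = 0.034657. Up to t*, 2.17 months. After t*, (0.9582 − 0.1294)/0.034657 = 23.91 months. W = 26.1.
- Lenalidomide: λ_PFS = 0.021460. Up to t*, 2.19 months. After t*, (0.9738 − 0.2818)/0.021460 = 32.25 months. W = 34.4.

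**Share of SPMs missed, 1 − W/A.**

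| Follow-up | Arm | A (months) | W (months) | Missed |
|---|---|---|---|---|
| 60 months | Placebo | 35.6 | 26.1 | 26.7% |
| 60 months | Lenalidomide | 42.8 | 34.4 | 19.6% |
| 84 months | Placebo | 41.6 | 28.2 | 32.3% |
| 84 months | Lenalidomide | 53.0 | 39.7 | 25.1% |

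With a 60-month minimum and an assumed uniform accrual of 24 to 84 months, the loss is 29.7-34.7% on placebo and 22.6-28.4% on lenalidomide.

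**Expected count ratio, lenalidomide:placebo, no drug effect on SPMs.**
- In the window: 34.4/26.1 = 1.32 at 60 months and 39.7/28.2 = 1.41 at 84 months.
- Over full follow-up: 42.8/35.6 = 1.20 and 53.0/41.6 = 1.27.

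**Does the direction of the loss hold?** All at 60 months:
- Adding assumed stopping hazards before progression of 0.05 per year on placebo and 0.1 to 0.3 per year on lenalidomide gives 32% missed on placebo against 33-51% on lenalidomide. The order reverses.
- Setting OS equal in both arms at a 36-month median, with PFS as designed, gives 26.7% against 3.4%. The gap widens the other way.

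**The case against.** The strongest reply is that the SAP never applies the treatment-emergent window to SPMs. A reader might infer that it does, because the paragraph attaches the abbreviation AEs to treatment-emergent events and SPMs then appear among AEs of special interest. The text does not support that inference. Section 12.1 opens with adverse events in general and defines the treatment-emergent set as a part of them. It foresees follow-up tables, and it says SPMs will be defined and summarized separately. After 30 days the protocol collects only drug-related serious events and SPMs, so SPMs would be a main content of any follow-up table. A redacted block in 12.1 may also bear on this. All of that stands: the documents show an unspecified window, not a decision to drop late SPMs. None of the visible text, however, fills the gap. Follow-up tabulation is discretionary, the definition is deferred without saying where, and deaths receive the firm follow-up commitment that SPMs do not.

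A reader might also infer that the window would remove mainly placebo cases, because placebo subjects progress sooner. The early-stopping calculation shows that this cannot be concluded. In addition, Amendment 10 ended placebo treatment and Amendment 11 stopped lenalidomide, so some last-dose dates were set administratively.

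Finally, most of the count imbalance comes from unequal survival rather than from the window, which raises the ratio by only about a tenth (1.32/1.20 = 1.10; 1.41/1.27 = 1.11). Under a constant hazard, a rate per person-time inside the window would be unbiased. That is correct, and it is why the missing denominator is part of the point: the visible plan offers no such rate.

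**Conclusion.** The point holds as a gap in specification with a practical consequence. The visible SAP does not say over what period SPMs are counted or against what time at risk, and the one numeric window within reach does not match the period of collection.

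If that window were used, about 20-32% of SPMs would be missed. This rests on the design medians being true, dosing to progression, a constant SPM hazard, and 60 to 84 months of follow-up. Early stopping would raise the loss; in the scenarios above it reaches about half on lenalidomide. A hazard that rises with time would also raise it, since late time is what is lost. The documents give no SPM incidence, no rate of stopping before progression and no accrual length, so neither the size nor the direction of the difference between arms is fixed.

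The denominator matters whichever window is chosen. Over full follow-up, crude counts would stand at about 1.20-1.27 to 1 with no drug effect, provided OS differs as designed. The underlying data are still collected as serious adverse events, so the problem lies in the summary and can be corrected.

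**What to change.** In SAP 12.1:
- State that SPMs are not limited to the treatment-emergent window.
- Summarize them by arm in the safety population from first dose to the end of survival follow-up. List separately any SPM between consent and first dose, since the protocol collects from consent.
- Report the rate per 100 person-years and the cumulative incidence with death as a competing event.
- Split onset into on-treatment and post-treatment, and state the cut-off used for the split.

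The cost is SAP wording and one added table. SPM and survival status are already collected in both arms every 24 weeks after treatment, so no new data are needed.
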